### 8.2.1 First Administration Period

- Admission the day prior to the visit for assuring 10.5-h fasting period.
- Dinner at least 10.5 h before the dosing in fasted condition or breakfast in fed condition.
- Subject's eligibility will be checked again before catheter insertion and drug's dosing.
- Catheter insertion at the moment of blood sampling for gonadotropins determination (elective, only for women).

**First day (treatment R):**

- At 5:00 h, grooming and intake of 250 mL of water.
- Between 05:20 and 06:30 h electrocardiogram.
- Following electrocardiogram the following activities will be performed:
  - ✓ Vital signs measurement.
  - ✓ Catheter insertion (control blood sampling).
  - ✓ Blood sampling for safety laboratory tests.
  - ✓ Finger stick for blood glucose determination.
  - ✓ Adverse events and prior medication.
  - ✓ Urine sampling for safety laboratory tests.
- At 08:00 h, oral administration of IMP with 250 mL of water at room temperature p.o., according to the standard operating procedure, code: **PPD** : PREPARATION AND ADMINISTRATION OF DRUGS IN INTERCHANGEABILITY AND BIOCOMPARABILITY CLINICAL STUDIES.
- From 08:30 to 00:00 h, sampling as per the schedule of assessments.
- At 09:00 h, intravenous administration of 10 mL of 10% glucose solution.
- At 10:00 h Measurement of blood glucose and capillary glucose on a test strip (hemoglucotest), 2 hours post dose and intravenous administration of 10 mL of 10% glucose solution.
- Finger stick and IV blood glucose, vital signs measurement 4 hours following dose.
- As from 12:00 h, breakfast.
- Finger stick for blood glucose determination and vital signs 8 hours following dose.
- As from 16:00 h, lunch.
- Finger stick and IV blood glucose, vital signs measurement 12 hours following dose.
- As from 21:00 h, dinner.

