## 7.2 Dosage and administration

The IMP (investigational medicinal product) will be given fast or fed state orally at a dose of Metformin 1000 mg/Gliclazide 30 mg (one tablet) with 250 mL of water. Only a single dose will be administered.

**Fast treatment:** subjects should fast for at least 10 hours before dosing. IMP will be dosed orally with 250 mL of water. No food intake is allowed for 4 hours following drug's dosing. Subjects be allowed water ad libidum except for 1 hour before and after drug administration.

**Fed treatment:** following night fasting for at least 10 hours, subjects should be provided the recommended food 30 minutes prior to the IMP dosing. They will be given 30 minutes as maximum for finalizing the food intake. IMP will be given 30 minutes following the start of food intake. Drug should be given with 250 mL of water. No food intake is allowed for 4 hours following drug's dosing. Subjects be allowed water as desired except for 1 hour before and after drug administration.

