### **8.1.3 Control of Meals and Liquid Intake**

Subjects from **R** treatment should fast for at least 10.5 hours before the dosing and at least for 4 hours following the dosing. The study drug will be administered (08:00 h). Water is allowed *ad libitum*, except for the period between one hour prior to dosing and the first meal.

Subjects from the **T'** treatment will have a standardized breakfast after a fast of at least 10.5 hours. Study subjects have to eat this meal in 30 minutes. 30 minutes after start of the breakfast the study drug will be administered (08:00 h). Water is allowed *ad libitum* 1 hours following the dose.

During the rest of confinement, meals will be served as shown below. Forty five minutes (45) will be allowed for having meals; water consumption will not be subject to this period.

*R' treatment's meals schedule*

MEALS	DAY 0 and 14,	DAY 1 and 15	DAY 2 and 16
Breakfast	-----	As from 07:30 h	As from 09:00 h
Lunch	-----	As from 16:00 h	As from 15:00 h
Dinner	21:00 h	As from 21:00 h	As from 20:00 h

*T treatment's meals schedule*

MEALS	DAY 0 and 14,	DAY 1 and 15	DAY 2 and 16,
Breakfast	-----	As from 12:00 h	As from 09:00 h
Lunch	-----	As from 16:00 h	As from 15:00 h
Dinner	21:00 h	As from 21:00 h	As from 20:00 h

Groups will be unsynchronized for 2 minutes among them for food delivery which is appropriate for the dosing order and interval.

Study breakfast consist of two fried eggs with butter, two bacon strips, two toasts with butter, 113 g of potato croquettes and 240 mL of whole milk (approximately 800 to 1000 calories) (150, 250, and 500-600 calories from protein, carbohydrate, and fat, respectively), substitutions in this test meal can be made as long as the meal provides a similar amount of calories from protein, carbohydrate, and fat and has comparable meal volume and viscosity. (FDA, 2002, EMA 2013).

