**First day (treatment T': food + drug):**

- At 5:00 h, grooming and intake of 250 mL of water.
- Between 05:20 and 06:30 h electrocardiogram.
- Following electrocardiogram the following activities will be performed:
  - ✓ Vital signs measurement.
  - ✓ Catheter insertion (control blood sampling).
  - ✓ Blood sampling for safety laboratory tests.
  - ✓ Finger stick for blood glucose determination.
  - ✓ Adverse events and prior medication.
  - ✓ Urine sampling for safety laboratory tests.
- At 7:30 h, breakfast. They will be given 30 minutes as maximum for food intake (FDA, 2002).
- At 08:00 h, oral administration of IMP with 250 mL of water at room temperature p.o., according to the standard operating procedure, code: **PPD** : PREPARATION AND ADMINISTRATION OF DRUGS IN INTERCHANGEABILITY AND BIOCOPARABILITY CLINICAL STUDIES.
- From 08:30 to 00:00 h, sampling as per the schedule of assessments.
- At 09:00 h, intravenous administration of 10 mL of 10% glucose solution.
- At 10:00 h Measurement of blood glucose and capillary glucose on a test strip (hemoglucotest), 2 hours post dose and intravenous administration of 10 mL of 10% glucose solution.
- Finger stick and IV blood glucose measurement 2 hours following dose.
- Finger stick and IV blood glucose, vital signs measurement 4 hours following dose.
- Finger stick for blood glucose determination and vital signs 8 hours following dose.
- As from 16:00 h, lunch.
- Finger stick and IV blood glucose, vital signs measurement 12 hours following dose.
- As from 21:00 h, dinner.

*Second day:*

- ⊕ At 8:00 h, 24.0-h sampling.
- ⊕ Finger stick for blood glucose determination, blood glucose and vital signs measurement 24 hours following dose.
- ⊕ As from 9:00 h, breakfast.
- ⊕ At 12:00 h, 28.0-h sampling.
- ⊕ As from 15:00 h, lunch.
- ⊕ Finger stick, IV blood glucose and vital signs measurement 32 hours following dose.
- ⊕ At 16:00 h, 32.0-h sampling.
- ⊕ As from 20:00 h, dinner.

*Third day:*

- ⊕ At 8:00 h, 48.0-h sampling and safety laboratory tests.
- ⊕ Physical examination.
- ⊕ Vital signs measurement.
- ⊕ Electrocardiogram.
- ⊕ Approximately at 10:30 h, temporary discharge from the clinical unit.

*Fourth day (ambulatory visit):*

- ⊕ At 8:00 h, 72.0-h sampling.

*Fifth day (ambulatory visit):*

- ⊕ At 8:00 h, 96.0-h sampling.

*Sixth day (ambulatory visit):*

- ⊕ At 8:00 h, 120.0-h sampling.

*Seventh day (ambulatory visit):*

- ⊕ At 8:00 h, 144.0-h sampling.

*Eight day (ambulatory visit):*

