## Appendix 2: Diet

Diet to be given to subjects following dose in each of the periods will be the same in quantity and content to that provided during the previous period.

Study breakfast: two fried eggs with butter, two bacon strips, two toasts with butter, 113 g of potato croquettes and 240 mL of whole milk (approximately 800 to 1000 calories) (150, 250, and 500-600 calories from protein, carbohydrate, and fat, respectively) (FDA, 2002, EMA 2013).

The rest of the diet (Breakfast day 2 and 16, Lunch and dinner) will be as shown in the following

Energetic Distribution			
Group	%	g	Kcal
Carbohydrates	55	275	1100
Proteins	15	75	300
Lipids	30	67	600
Total Kcal	---	---	2000

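### The dosing-day schedules give a meal 4 hours after dosing only in the fasted condition, so the fed/fasted ratios may carry an avoidable difference in post-dose meals and water

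*Protocol*

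**What the plan says.** The places that bear on dosing-day meals and water are these.

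- **Protocol 8.2.1, fasted day (R):** dose at 08:00, then "As from 12:00 h, breakfast", lunch from 16:00 and dinner from 21:00.
- **Protocol 8.2.1, fed day (T'):** "At 7:30 h, breakfast. They will be given 30 minutes as maximum for food intake", dose at 08:00, lunch from 16:00 and dinner from 21:00. No 12:00 meal is listed.
- **Protocol 8.1.3, meal tables:** the same clock times for days 1 and 15. The headings (R' and T) do not match the labels in the text (R fasted, T' fed), but the times agree with 8.2.1.
- **Protocol 8.1.3, water:** when fasted, free access "except for the period between one hour prior to dosing and the first meal"; when fed, free access from 1 hour after the dose.
- **Protocol 7.2:** the same two rules in both conditions. For food, "No food intake is allowed for 4 hours following drug's dosing". For water, in the fasted wording, "Subjects be allowed water ad libidum except for 1 hour before and after drug administration"; the fed wording is equivalent.
- **Protocol Appendix 1, footnote 8:** covers fasting and fed dosing, and has a standardized lunch once 4 hours without food have passed.
- **Protocol Appendix 2:** "Diet to be given to subjects following dose in each of the periods will be the same in quantity and content" as in the previous period. It describes the study breakfast ("approximately 800 to 1000 calories") and continues: "The rest of the diet (Breakfast day 2 and 16, Lunch and dinner) will be as shown in the following".
- **Protocol 6.2:** names the timetable, kind and quantity of food among the confounders to be controlled.

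**The concern.** The primary results are six fed/fasted ratios: Cmax, AUC0-t and AUC0-∞ for two analytes. Under 8.1.3 and 8.2.1 the two conditions differ in more than the test meal before the dose. Fasted subjects also eat at +4 h, when fed subjects do not, and under 8.1.3 they go without water for longer. This difference goes with treatment in every subject, in both sequences and both periods. Whatever it does to absorption is therefore absorbed into the treatment effect. The tablet is a modified-release product, and the meal falls inside the sampling window that the protocol itself marks as being around Cmax.

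**Working it through.** **The plan's own precision, as a yardstick.** Protocol 9.1 assumes a CV of 20% and 18 evaluable subjects, and gives 90% limits of 0.89R to 1.12R. Taking the CV as within-subject, s = √ln(1 + 0.20²) = 0.198. The log-scale half-width is t(0.95; 16 df) × s × √(2/18) = 1.746 × 0.198 × 0.333 = 0.115. Then exp(±0.115) gives 0.891 and 1.122, so the figure reproduces. The present point does not alter it.

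**Meals relative to the 08:00 dose (8.1.3 tables and 8.2.1).**

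| | Fasted | Fed |
|---|---|---|
| Test meal | none | 07:30 (−0.5 h) |
| 12:00 | breakfast (+4 h) | none |
| 16:00 | lunch (+8 h) | lunch (+8 h) |
| 21:00 | dinner (+13 h) | dinner (+13 h) |
| Post-dose meals | 3 | 2 |
| Meals over the whole day | 3 | 3 |

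The 4-hour food rule in 7.2 is the same in both conditions, so it permits a 12:00 meal when fed and does not explain the difference.

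**Content of the 12:00 breakfast.** Appendix 2 gives the ordinary diet for breakfast on days 2 and 16, and for lunch and dinner. The only other breakfast it describes is the study breakfast. The content of the fasted 12:00 breakfast on days 1 and 15 is therefore not clearly defined, and the high-fat meal cannot be ruled out.

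**Samples affected by the meal difference.** Protocol 8.6 has 21 post-dose samples. Appendix 1 places PK sampling before a meal due at the same time, so the 4 h sample precedes the 12:00 meal and the 8 h sample precedes lunch. The samples at 5, 6, 7 and 8 h (4 of 21) are drawn when only fasted subjects have eaten since dosing. Of the four samples marked as near Cmax (3, 4, 5 and 6 h), two fall in this interval.

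**Water.** Under 8.1.3, fasted subjects have none from 07:00 to 12:00 (5 h, apart from the 250 mL taken with the dose), while fed subjects may drink from 09:00. Access is unequal for 3 h, 09:00 to 12:00, which holds the 2, 3 and 4 h samples. Under 7.2 the restriction is 07:00 to 09:00 in both conditions and there is no difference. So this part exists only if 8.1.3 overrides 7.2. If it does, 3 + 4 = 7 of 21 samples fall under unequal water or meals.

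**Model.** Protocol 9.5 and SAP 15.1 fit treatment, period and sequence as fixed effects and subject within sequence as random. None of these separates the test meal from a later difference tied to treatment. The 90% interval, built on residual error, does not cover such a difference.

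**Is +4 h pharmacokinetically relevant?** The documents are mixed.
- *For:* 8.6 marks 3–6 h as near Cmax. Section 3.2.2 has gliclazide rising to 6 h and level from 6 to 12 h. Section 3.1.2 gives a 7 h peak for metformin XR 500 mg, a different strength.
- *Against:* 8.6 labels 7 h onward as elimination. Section 3.1.5 gives a metformin peak near 2 h, formulation not stated. Section 3.2.2 calls gliclazide fully absorbed, which speaks against an effect on its AUC.

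**Scale, on assumed shifts only.** The documents give no effect for the +4 h meal. Suppose it multiplied fasted exposure by (1 + b). The observed ratio is then multiplied by 1/(1 + b). Coverage of the ratio without that meal effect comes from a noncentral t with 16 df and noncentrality −ln(1 + b) / (0.198 × 0.333).

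| Assumed b | Ratio multiplied by | Coverage of the nominal 90% interval |
|---|---|---|
| +5% | 0.952 | 82% |
| +10% | 0.909 | 60% |
| +15% | 0.870 | 35% |
| −5% | 1.053 | 81% |
| −10% | 1.111 | 55% |
| −15% | 1.176 | 24% |

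A shift of about 10% would be nearly as large as the planned 12% precision. Nothing in the documents says that a shift of any of these sizes occurs.

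**The case against.** The strongest reply has four parts.

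1. *The protocol does describe a +4 h meal for both groups.* Appendix 1 footnote 8 does. That stands as text, so the protocol as a whole is inconsistent rather than uniformly one-sided. Its weight is limited. Appendix 1 carries the title of a bioequivalence trial with a different design, and the same footnote differs from 7.2 on the dosing water (240 against 250 mL) and the time allowed for the meal (25 against 30 minutes). The detailed schedules in 8.1.3 and 8.2.1 agree with each other and do not follow it.

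2. *Appendix 2 need not be breached.* It lists the study breakfast, which fed subjects eat before the dose, within the diet it introduces as following the dose, so it may mean the whole dosing day. On that reading each condition has three meals and only breakfast timing moves; Appendix 2 promises quantity and content, not timing. This reading is available. The literal one, under which post-dose intake differs, is available too.

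3. *The objective is a fed against a fasted state, not the isolated effect of one meal.* Correct. Inability to separate a feature tied to treatment is also not a fault of the model. But 6.2 sets out to control the timetable and quantity of food, and this difference is not needed to create the two states.

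4. *No bias is shown.* Also correct. The sample counts show where samples fall, not that any parameter moves.

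**Conclusion.** The point holds as an avoidable, treatment-linked difference in the operative schedules, together with a conflict between sections that leaves the intended diet and water rule unclear. If 8.1.3 and 8.2.1 are followed, the six primary ratios compare two dosing-day meal schedules: 3 against 2 post-dose meals, with 4 of 21 samples in the interval where only fasted subjects have eaten since dosing. If 8.1.3 also governs water, 3 further samples are affected. The size and direction of any effect are unknown. It is worth fixing because the remedy is cheap, not because a distortion has been demonstrated.

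Two stronger readings are tempting and are not supported. A reader might infer that 8.2.1 and Appendix 2 cannot both have been followed, and so that the SAP 12.1 statement of no deviations must be wrong. The whole-day reading of Appendix 2 leaves room for both; the SAP statement simply does not tell us which meals were served. A reader might also infer that the fed/fasted ratios are biased. The evidence on whether +4 h matters is mixed, and the assumed shifts above are illustration only.

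**What to change.** - In 8.1.3 and 8.2.1, serve the same standardized meal, not the test meal, at 12:00 (+4 h) in both conditions, as Appendix 1 footnote 8 already describes. Define its content and amount in Appendix 2. Keep the 16:00 lunch and 21:00 dinner identical.
- Apply the 7.2 water rule to both conditions in 8.1.3.
- Align 8.1.3 (including its table headings), 8.2.1 and Appendices 1 and 2.
- Do not equalise by deleting the fasted 12:00 meal. That would lengthen the fast from 15 h (21:00 to 12:00) to 19 h (21:00 to 16:00) in healthy subjects given a sulphonylurea, and Protocol section 4 warns of hypoglycemia when meals are skipped.

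The cost is one extra meal per subject in the fed period (22 in all) and some wording, with no added visits, samples or subjects. The downside is a fourth meal on the fed dosing day. Post-dose meals become 3 against 3, and the gap after the start of the test meal shortens from 8.5 h to 4.5 h.

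For the completed trial (SAP 8: 22 randomized, 21 finished), the report should state which meals and water rules were actually applied and when. If 8.2.1 was followed, it should add that the ratios compare two dosing-day meal schedules. That takes one or two sentences.

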**First day (treatment T': food + drug):**

- At 5:00 h, grooming and intake of 250 mL of water.
- Between 05:20 and 06:30 h electrocardiogram.
- Following electrocardiogram the following activities will be performed:
  - ✓ Vital signs measurement.
  - ✓ Catheter insertion (control blood sampling).
  - ✓ Blood sampling for safety laboratory tests.
  - ✓ Finger stick for blood glucose determination.
  - ✓ Adverse events and prior medication.
  - ✓ Urine sampling for safety laboratory tests.
- At 7:30 h, breakfast. They will be given 30 minutes as maximum for food intake (FDA, 2002).
- At 08:00 h, oral administration of IMP with 250 mL of water at room temperature p.o., according to the standard operating procedure, code: **PPD** : PREPARATION AND ADMINISTRATION OF DRUGS IN INTERCHANGEABILITY AND BIOCOPARABILITY CLINICAL STUDIES.
- From 08:30 to 00:00 h, sampling as per the schedule of assessments.
- At 09:00 h, intravenous administration of 10 mL of 10% glucose solution.
- At 10:00 h Measurement of blood glucose and capillary glucose on a test strip (hemoglucotest), 2 hours post dose and intravenous administration of 10 mL of 10% glucose solution.
- Finger stick and IV blood glucose measurement 2 hours following dose.
- Finger stick and IV blood glucose, vital signs measurement 4 hours following dose.
- Finger stick for blood glucose determination and vital signs 8 hours following dose.
- As from 16:00 h, lunch.
- Finger stick and IV blood glucose, vital signs measurement 12 hours following dose.
- As from 21:00 h, dinner.

*Second day:*

- ⊕ At 8:00 h, 24.0-h sampling.
- ⊕ Finger stick for blood glucose determination, blood glucose and vital signs measurement 24 hours following dose.
- ⊕ As from 9:00 h, breakfast.
- ⊕ At 12:00 h, 28.0-h sampling.
- ⊕ As from 15:00 h, lunch.
- ⊕ Finger stick, IV blood glucose and vital signs measurement 32 hours following dose.
- ⊕ At 16:00 h, 32.0-h sampling.
- ⊕ As from 20:00 h, dinner.

*Third day:*

- ⊕ At 8:00 h, 48.0-h sampling and safety laboratory tests.
- ⊕ Physical examination.
- ⊕ Vital signs measurement.
- ⊕ Electrocardiogram.
- ⊕ Approximately at 10:30 h, temporary discharge from the clinical unit.

*Fourth day (ambulatory visit):*

- ⊕ At 8:00 h, 72.0-h sampling.

*Fifth day (ambulatory visit):*

- ⊕ At 8:00 h, 96.0-h sampling.

*Sixth day (ambulatory visit):*

- ⊕ At 8:00 h, 120.0-h sampling.

*Seventh day (ambulatory visit):*

- ⊕ At 8:00 h, 144.0-h sampling.

*Eight day (ambulatory visit):*

- ⊕ At 8:00 h, 168.0-h sampling.
- ⊕ Approximately at 10:00 h, temporary discharge and free appointment.

### **8.2.2 Washout Period**

Washout period lasts for 14 days after first dosing. It is intended to clear the prior dose before administering the next one and to fulfill with the NOM-177-SSA1-2013 criterion about having a period of at least 7 half-lives for the study drug.

### **8.2.3 Second Administration Period**

Analogous to the First period of treatment after a 14 days wash-out period

### **8.2.4 End of Trial (EoT)**

- ⊕ At 08:00 h, 168.0-h sampling.
- ⊕ Weight measurement for each subject.
- ⊕ Blood for qualitative and quantitative pregnancy test in childbearing potential women.
- ⊕ Blood sampling for safety laboratory tests.
- ⊕ Urine sampling for safety laboratory tests.
- ⊕ Physical examination.
- ⊕ Vital signs measurement.
- ⊕ Electrocardiogram.
- ⊕ Approximately at 11:00 h, temporary discharge and free appointment.

### **8.3 Baseline demographic characteristics**

At screening (within 21 days before first administration), the following demographic data will be collected: date of birth, sex (gender), race, and ethnicity  
Specify any additional critical variables to be assessed such as:

- Information about previous and concomitant medications
- Medical history data including medication history

- Weight, height and BMI
- Special diets
- For women, menstrual status and date of last menstrual period.
- Month prior to drug administration, nicotine consumption
- Smoking history
- Alcohol consumption
- Caffeine or xanthine consumption -containing beverages, intake of grapefruit, orange, cranberry or juices of these three fruits, intake of food containing xanthine and usual diet.
- Physical examination, and serum virology
- Safety laboratory
- ECG
- Vital signs

#### **8.4 Efficacy assessments**

Not applicable.

#### **8.5 Safety Assessments**

Clinical safety will be assessed by means of a complete physical examination (at SCR, before each IMP administration and 48 and 168 h after each dose). On the other hand, throughout the study, subjects will be continuously monitored, including vital signs measurements (baseline and 4, 8, 12, 24, 32, 48 and 168 h post-dose) and electrocardiograms will be performed (baseline, 48 and 168 h post-dose). All examinations 168 h after second administration correspond to the EOT examination.

Safety will be assessed by means of full laboratory tests (at screening, at each baseline and 48 h after each administration) (hematology, clinical chemistry, coagulation, and urinalysis). In blood analyses besides glucose (baseline, 2, 4, 12, 24, and 32 post-dose), finger-stick glucose (Hematoglucotest) will be monitored (baseline, 2, 4, 8, 12 and 24 h post-dose), see flow chart.

Investigational drugs' safety profile will be assessed by means of the record, report and analysis of baseline medical conditions, including the use of drugs, smoking habits and alcohol use, adverse events, findings in the physical examination, including vital signs, drug abuse screening, pregnancy test and laboratory tests including hematology, clinical chemistry, coagulation, urinalysis).

Comprehensive assessment for any apparent toxicity experience by any subject should be carried out since informed consent signature and throughout the study. The Principal Investigator will report any adverse event, observed by him/her or the assigned medical staff or reported by the subject (see section 8.5.1.2). Reporting period for adverse events is described in section 8.5.1.3.

## **8.5.1 Adverse Event**

### **8.5.1.1 Adverse Event Definitions**

#### **Adverse Event**

An adverse event is any untoward medical occurrence which may occur during drug's clinical research stage but which do not necessarily has a causal relation with the drug. Therefore, an adverse event can be any untoward sign and symptom (including any abnormal finding in the laboratory tests), or condition temporarily related to the use of the drug (investigational), whether related or not to that product.

Adverse events associated to the use of drugs in humans, related or not to the drug, include the following:

- ✚ Any adverse event occurring during the use of the drug in the professional practice.
- ✚ An adverse event which occurs because of the abuse of drug products or substances.
- ✚ An adverse event which occur following the stop of drug's intake.
- ✚ An adverse event where there is a reasonable possibility that the event occurred only as a consequence of the subject's participation in the study (e.g., adverse event or serious adverse event due to the stop of anti-hypertensive drugs during wash-out phase) should be reported as an adverse event even though this is not related to the investigational product.
- ✚ Clinical onset on any failure of the expected pharmacological action.

In case the event meets the criteria for "serious" adverse event, it should be recorded and reported as that.

